6.4.1.1.2 Anti-diarrheal treatment with midostaurin

For the management of diarrhea, oral loperamide can be administered. An initial dose of 4 mg followed by 2 mg every 4 hours or after every unformed stool (maximum of 16 mg/day) is

suggested. However, the kind and dose of anti-diarrheal should be chosen per investigator discretion.

6.4.1.1.3 Liver toxicity management with midostaurin

As midostaurin is extensively metabolized by the liver, patients with significantly impaired liver function or with hepatic failure should not receive midostaurin. Monitoring of LFTs (transaminases and bilirubin) is recommended particularly when used in combination with chemotherapeutic regimens that are known to be associated with increased hepatic risk. Labels for both daunorubicin and cytarabine contain hepatotoxicity warnings.

6.4.1.1.4 Ocular toxicity management during consolidation

For the management of ocular toxicity during consolidation administer 0.1% Dexamethasone or other corticosteroid ophthalmic solution 2 drops to each eye 4 times a day to begin 6-12 hours prior to the initiation of the cytarabine infusion and to continue for at least 24 hours after the last cytarabine dose.

6.4.1.2 Contraceptives with midostaurin

Women must avoid breast-feeding during study treatment, and all women of childbearing potential will be required to employ a highly effective method of birth control, refer to [Section 5.3](#), which is defined as a birth control which results in a low failure rate (i.e. less than 1% per year) when used consistently and correctly. This has to be employed for the duration of the study and for 4 months post study because of the long half-life of the metabolite, CGP52421.

6.4.2 Permitted concomitant therapy requiring caution and/or action

6.4.2.1 Concomitant medications with potential for CYP3A4 interactions

6.4.2.1.1 Midostaurin can be impacted by CYP3A4 inhibitors and inducers:

Midostaurin is a sensitive substrate of CYP3A4. This indicates that the pharmacokinetics of midostaurin may be influenced by drugs that are inducers or inhibitors of CYP3A4.

6.4.2.1.2 Interactions with inhibitors of cytochrome P450 3A4

In a healthy volunteer drug-drug interaction study (A2109) where midostaurin was co-administrated with the potent CYP450 3A4 inhibitor ketoconazole, at steady-state of ketoconazole, midostaurin C_{max} increased by 1.8-fold, AUC_{inf} by 10-fold.

Another study, [\[CPKC412A2104E2\]](#), evaluated two midostaurin dosing regimens with an intra-patient dose escalation of midostaurin up to 600 mg/day (300mg b.i.d, N=12) and concomitant administration of midostaurin 50 mg b.i.d with itraconazole as an inhibitor of CYP3A4 enzymatic activity in a subset of patients (N=12). The study could not establish a maximum tolerated dose, suggesting that exposure to a midostaurin dose of up to 600mg/day was deemed tolerable. Moreover, the itraconazole cohort of the study did not indicate overt increase in midostaurin steady-state concentration, as only three patients showed a 2-3 fold increase in their steady-state C_{min} .

Taken together, the data indicates that co-administration of strong CYP3A4 inhibitors with midostaurin has the potential to increase exposure of midostaurin.

Based on the above data, administration of concomitant strong CYP3A4 inhibitors with midostaurin should be avoided and alternative therapeutics, which does not strongly inhibit CYP450 3A4 activity, should be considered.

Please see [Section 6.4.2.2](#) for the suggested antifungal regimens.

Here below is a list of strong CYP3A4 inhibitors:

clarithromycin, telithromycin, troleandomycin, indinavir, lopinavir, nelfinavir, ritonavir, saquinavir, tipranavir, itraconazole, ketoconazole, posaconazole, voriconazole, boceprevir, telaprevir, cobicistat, conivaptan, nefazodone.

A list of moderate CYP450 3A4 can be found on:

[//medicine.iupui.edu/clinpharm/ddis/main-table/](http://medicine.iupui.edu/clinpharm/ddis/main-table/)

6.4.2.1.3 Interactions with moderate and strong inducers of cytochrome P450 3A4

In a healthy volunteer drug-drug interaction study (A2110) where midostaurin was co-administrated with the potent CYP450 3A4 inducer rifampicin, the C_{max} and AUC of midostaurin decreased by 73% and 94%, respectively. To avoid sub-therapeutic exposure to midostaurin, moderate or potent CYP450 3A4 inducers should not be co-administered.

Strong CYP3A4 inducers: avasimibe, carbamazepine, mitotane, phenobarbital, phenytoin, rifabutin, rifampin (rifampicin), St. John's wort (*hypericum perforatum*).

Moderate CYP3A4 inducers: bosentan, efavirenz, etravirine, genistein, modafinil, nafcillin, ritonavir, talviraline, thioridazine, tipranavir.

6.4.2.1.4 Midostaurin not expected to affect the pharmacokinetics of other CYP3A4 substrates:

In study A2112, Midostaurin at a single dose of 100 mg was administered concomitantly with midazolam on Day 3 and, then 50 mg twice daily from Day 4 to Day 6. Overall, the PK of midazolam (sensitive CYP3A4 probe) or its metabolite 1'-hydroxymidazolam were not affected in a clinically meaningful manner following four dosing days of midostaurin in healthy subjects.

As a result, midostaurin is neither a CYP3A4 inhibitor nor a CYP3A4 inducer *in vivo* in humans at clinically relevant conditions. Therefore, midostaurin is not expected to affect the pharmacokinetics of other CYP3A4 substrates.

6.4.2.2 Concomitant anti-infective prophylaxis and treatment

It is highly recommended to avoid concomitant strong CYP3A4 inhibitors (e.g. ketoconazole, itraconazole, voriconazole, posaconazole). The suggested antifungal regimens from a drug metabolism perspective are described below:

Prophylaxis

- Fluconazole (moderate CYP3A4 inhibitor)

- Micafungin

If a patient requires active treatment for a fungal or mold infection and the only treatment options is an azole that is a strong CYP3A4 inhibitor, then the suggested agents from a drug metabolism and safety perspective include:

Treatment

- Voriconazole
- Posaconazole

These are both strong CYP3A4 inhibitors and will likely increase midostaurin concentrations; therefore, patients should be monitored closely for signs of increased toxicity.

6.4.3 Prohibited concomitant therapy

There is no prohibited concomitant therapy, however, as described in [Section 6.4.2](#), it is highly recommended to avoid concomitant strong CYP3A4 inhibitors.

6.4.4 Use of bisphosphonates (or other concomitant agents)

Not Applicable

6.5 Patient numbering, treatment assignment or randomization

6.5.1 Patient numbering

Each patient is identified in the study by a Subject Number (Subject No.), that is assigned when the patient is first enrolled for screening and is retained as the primary identifier for the patient throughout his/her entire participation in the trial. The Subject No. consists of the Center Number (Center No.) (as assigned by Novartis to the investigative site) with a sequential subject number suffixed to it, so that each subject is numbered uniquely across the entire database. Upon signing the informed consent form, the patient is assigned to the next sequential Subject No. available to the investigator through the Oracle Clinical RDC interface.

Once assigned, the Patient No. must not be reused for any other patient and the Patient No. for that individual must not be changed, even if the patient is re-screened. If the patient fails to be dosed, the reason will be entered into the Screening Log page.

6.5.2 Treatment assignment

Patients who fulfill all entry criteria will receive midostaurin (investigational drug) on day 8 of the first induction cycle.

6.5.3 Treatment blinding

Not Applicable

6.6 Study drug preparation and dispensation

The Investigator or responsible site personnel must instruct the patient or caregiver to take the study treatment as per protocol. Study treatment will be dispensed to the patient by authorized

site personnel only. All dosages prescribed to the patient and all dose changes during the study must be recorded on the Dosage Administration Record eCRF.

Table 6-5 Preparation and dispensing

Study treatments	Dispensing	Preparation
Midostaurin (PKC412)	Soft Gelatin Capsules (SGC) including instructions for administration are dispensed by study personnel on an outpatient basis. Patients will be provided with adequate supply of study treatment for self-administration at home until at least their next scheduled study visit.	Not applicable
Daunorubicin	Not applicable	Refer to local product information
Idarubicin	Not applicable	Refer to local product information
Cytarabine	Not applicable	Refer to local product information

6.6.1 Study treatment packaging and labeling

Midostaurin will be provided as global supply by Novartis Drug Supply Management. Midostaurin will be supplied via a blister pack, with a study specific label. Labeling of these supplies will be done at global level under the responsibility of Novartis DSM.

Medication labels will be in the local language and comply with the legal requirements of each country. They will include storage conditions for the drug and study number but no information about the patient.

6.6.2 Drug supply and storage

Study drug (midostaurin) must be received by designated personnel at the study site, handled and stored safely and properly, and kept in a secured location to which only the investigator and designated site personnel have access. Upon receipt, midostaurin should be stored according to the instructions specified on the drug labels and in the [Investigator's Brochure].

Table 6-6 Supply and storage of study treatments

Study treatments	Supply	Storage
Midostaurin (PKC412)	Centrally supplied by Novartis	Per label requirements

6.6.3 Study drug compliance and accountability

6.6.3.1 Study drug compliance

Compliance will be assessed by the investigator and/or study personnel at each patient visit and information provided by the patient and/or caregiver will be captured in the Drug Accountability Form. This information must be captured in the source document at each patient visit.

6.6.3.2 Study drug accountability

The Treating Investigator or designee must maintain an accurate record of the shipment and dispensing of study treatment in a drug accountability log. Drug accountability will be noted by the field monitor during site visits and at the completion of the study. Patients will be asked to

return all unused study treatment and packaging on a regular basis, at the end of the study or at the time of study treatment discontinuation.

At study close-out, and, as appropriate during the course of the study, the investigator will return all used and unused study treatment, packaging, drug labels, and a copy of the completed drug accountability log to the Novartis monitor or to the Novartis address provided in the investigator folder at each site.

6.6.3.3 Handling of other study treatment

Not applicable.

6.6.4 Disposal and destruction

The study drug supply can be destroyed at the local Novartis facility, Drug Supply group or third party, as appropriate.

Please do not destroy any study drug until your monitor has had the opportunity to review your inventory and complete drug accountability reconciliation. If your site cannot destroy the drug locally, you can return it to a designated Novartis vendor for safe destruction. Please discuss this process with your monitor.

7 Visit schedule and assessments

7.1 Study flow and visit schedule

Table 7-1 lists all of the assessments and indicates with an “X”, the visits when they are performed. All data obtained from these assessments must be supported in the patient’s source documentation.

Note: If treatment with midostaurin is withheld at any time, all study visits, and safety assessments should continue according to the appropriate study days from Day 1 of each cycle as per the schedule of assessments.

All data obtained from these assessments must be supported in the patient’s source documentation. No eCRF will be used as a source document. The table indicates which assessments produce data to be entered into the database (D) or remain in the source documents (S).

The number of cycles in each phase (induction, consolidation and maintenance) is decided on at the discretion of the investigator, based on the patient’s clinical status.

Table 7-1 Visit evaluation schedule

	Category	Protocol Section	Screening / Baseline	Induction Phase Up to 2 cycles (Pre-dose/cycle)			Consolidation Phase Up to 4 Cycles (pre-dose/cycle)							Maintenance Phase Up to 12 Cycles (pre-dose/cycle)	End of Study Treatment	30 Day Safety Follow up								
Visit Name			(C1D1 - C1D7)	C1D8 Enrollment	C2D1	C2D8	C1D1	C1D8	C2D1	C2D8	C3D1	C3D8	C4D1	C4D8	C1D1 up to C12D1									
Study day(s)			-1	1																				
Cycle Days			7	8	1	8	1	8	1	8	1	8	1	8	1	1	Last							
FLT3 mutation status known (ITD/TKD)	D	7.1.2.	X																					
NPM1 mutation	D	4.1.	NPM1 mutation status will be collected if available																					
Prior and Concomitant Medications	D	7.1.2.3.	X	X			X							X	X									
Surgical and Medical Procedures	D	7.1.2.3.	X	X			X							X	X									
Physical examination	S	7.2.2.1.	X	X			X							X	X									
Height	D	7.2.2.3.	X												X									
Weight	D	7.2.2.3.	X	X			X							X	X									
Vital signs	D	7.2.2.2.	X	X			X							X	X									
ECOG Performance status	D	7.2.2.4.	X												X									
Laboratory assessments (local lab)																								
Hematology	D	7.2.2.5.1	X	For CR/CRI assessments and when justified for the assessment of a treatment related AE or SAE and at physician's discretion																				

	Category	Protocol Section	Screening / Baseline	Induction Phase Up to 2 cycles (Pre-dose/cycle)			Consolidation Phase Up to 4 Cycles (pre-dose/cycle)						Maintenance Phase Up to 12 Cycles (pre-dose/cycle)	End of Study Treatment	30 Day Safety Follow up		
Visit Name			(C1D1 - C1D7)	C1D8 Enrollment	C2D1	C2D8	C1D1	C1D8	C2D1	C2D8	C3D1	C3D8	C4D1	C4D8	C1D1 up to C12D1		
Study day(s)			-1	1													
Cycle Days			7	8	1	8	1	8	1	8	1	8	1	8	1	1	Last
Chemistry	D	7.2.2.5.	X	When justified for the assessment of a treatment related AE or SAE and at physician's discretion													
Urinalysis	D	7.2.2.5.	X														
Coagulation	D	7.2.2.5.	X														
Blood transfusion	D	6.4.1.		To be captured in the eCRF during the study													
Pregnancy test	D	7.2.2.5.3		Within 2 days prior to midostaurin dosing in induction and consolidation phase.										X	X		
Chest x-ray	D	7.2.2.6.	X														
ECG	D	7.2.2.7.1	X		X	X	X	X	X	X	X	X	X	X	X	X	
Cardiac Imaging (LVEF)	D	7.2.2.7.2	X	When justified for the assessment of a treatment related AE or SAE and at physician discretion											X		
	Safety																
Adverse events	D	8.1.		To be recorded continuously													
	Study treatment																
Study treatment administration	D	6.6.		X					X				X	X	X	X	X
	Other assessments																

	Category	Protocol Section	Screening / Baseline	Induction Phase Up to 2 cycles (Pre-dose/cycle)			Consolidation Phase Up to 4 Cycles (pre-dose/cycle)							Maintenance Phase Up to 12 Cycles (pre-dose/cycle)	End of Study Treatment	30 Day Safety Follow up	
Visit Name			(C1D1 - C1D7)	C1D8 Enrollment	C2D1	C2D8	C1D1	C1D8	C2D1	C2D8	C3D1	C3D8	C4D1	C4D8	C1D1 up to C12D1		
Study day(s)			-1	1													
Cycle Days			7	8	1	8	1	8	1	8	1	8	1	8	1	1	Last
Resource utilization	D	7.2.5.												X	X		
Bone marrow aspiration	D		Please refers to Section 7.1.2	To be performed between Day 21 to Day 28 at each cycle			Prior to first consolidation cycle C1D1, and if necessary per investigator's decision during the consolidation phase							Prior to first maintenance cycle C1D1 and every 3 months	X		
CR/CRi	D	7.2.1.		Day 21-28 for each induction cycle.			CR/CRi in induction, consolidation and maintenance therapy is collected as secondary endpoint. Prior to first consolidation cycle and If necessary per investigator's decision during the consolidation phase							Prior to first maintenance cycle C1D1 and every 3 months	X		

7.1.1 Molecular pre-screening

Not Applicable

7.1.2 Screening

Patients who are newly diagnosed with AML, have a known FLT3 ITD or TKD mutation and who have already started a “7+3” or “5+2” chemotherapy regimen in first induction will be consented and screened during the screening/baseline period (between C1D1 (chemotherapy already started) to C1D7) at least all the activities should be completed at Day 7 of the first chemotherapy (at Day -1). Re-screening is not allowed in this study.

The historical BMA result used to diagnose AML to the patients can be considered a part of inclusion criteria in the study.

If an historical BMA is available within 15 days before C1D1 of the first chemotherapy there is no need to repeat this assessment during the screening/baseline period.

If in case an historical BMA is not available within the 15 days before C1D1 of the first chemotherapy, a BMA should be performed during the screening/baseline period of the study.

7.1.2.1 Eligibility screening

Following registering in the IRT for screening, patient eligibility will be checked once all screening procedures are completed. The eligibility check will be embedded in the IRT system. Please refer and comply with detailed guidelines in the IRT manual.

Screening assessments should be performed at the time of the screening except for pregnancy test if result is available and negative within 7 days prior to screening, or for cardiac imaging and chest x ray if results are within 14 days prior to screening.

7.1.2.2 Information to be collected on screening failures

Patient who signed an Informed Consent Form but failed to start on midostaurin for any reason will be considered as a screen failure. The reason for not being started on midostaurin will be entered on the Screening Phase Disposition eCRF. The demographic information, informed consent, and Inclusion/Exclusion pages must also be completed for Screen Failure patients. No other data will be entered into the clinical database for patients who are screen failures, unless the patient has a Serious Adverse Event during the Screening Phase (see [Section 8.2](#) for SAE reporting details). The following eCRFs must be completed for screening failure patients:

- Screening Phase Disposition page
- Informed consent
- Demography
- Adverse Events (only if an SAE occurs. Refer to [Section 8.2](#).)
- Inclusion/Exclusion Criteria

7.1.2.3 Patient demographics and other baseline characteristics

Baseline patient data pertaining to demographic information and relevant medical history related to study indication should be documented accordingly in the eCRFs including, but not limited to, the following information:

- Demography (including: date of birth, age, patient initials, gender, childbearing potential, race and ethnicity, or as allowed by local regulations)
- Relevant medical history
- Date of diagnosis
- Physical Examination (Height, Weight, Vital Signs)
- Performance status
- FLT3 mutation status (ITD or TKD)
- Bone marrow aspiration
- Any additional mutation information, if known
- Prior and Concomitant Medications
- Surgical and Medical Procedures
- Chemotherapy information from induction cycle 1 day 1 to day 7

Additionally all other medications and significant non-drug therapies taken within 28 days prior to the first dose of midostaurin being administered must be recorded on the eCRF page and updated on a continual basis if there are any new changes to the medication. Medications include Investigator prescriptions and over-the-counter medications, vitamins, and herbal and alternative therapies.

Information to be collected on concomitant medications/significant non-drug therapies will include the following:

- Medication/Non-drug therapy trade name
- Reason for medication
- Start/End date and if continuing at time of examination

7.1.3 Run-in period

Not Applicable

7.1.4 Treatment period

Patients will begin midostaurin after completing all screening procedures and fulfilling all of the eligibility criteria. The study design is outlined in [Figure 4-1](#) and [Figure 4-2](#) by treatment phase; induction; consolidation; maintenance. Patients achieving CR/CRI following 1 to 2 cycles of induction will continue to consolidation therapy for up to 4 cycles. Patients who maintain a CR/CRI following consolidation may continue to the maintenance phase up to 12 cycles. The duration of each phase may vary based on investigator discretion. Patients will be treated on protocol for about 18 months. Patients may be removed from treatment due to unacceptable toxicity, disease progression, at the discretion of the Investigator, withdrawal of consent, or as explained in [Section 7.1.3](#), whichever comes first.

For details of assessments, refer to [Table 7-1](#).

7.1.4.1 Induction phase

Newly diagnosed AML patients will receive “7+3” or “5+2” induction therapy with cytarabine and daunorubicin (or idarubicin) as defined by NCCN treatment guidelines ([NCCN Guidelines v1.2017](#)). Enrolled patients will subsequently receive oral midostaurin 50 mg (two 25 mg capsules) twice a day on days 8-28 (see [Table 6-1](#)). Patients should take their doses at approximately the same time each day, and approximately 12 hours should elapse between the morning and evening doses. Each daily dose should be given with food and a glass of water (~240 mL). Patients should be instructed to swallow capsules whole and not chew capsules. If vomiting occurs, no re-dosing is allowed prior to the next scheduled dose.

A switch between regimens is not allowed.

Refer to [Table 6-1](#) for Induction treatment schedule.

Patients who achieved a CR/CRI after the first cycle may continue with the consolidation phase, all other patients may get a second induction cycle as per investigator’s discretion.

Second induction cycle

For patients requiring a second induction cycle, treatment will begin at least 3 days and no later than 42 calendar days after completing midostaurin. The treatment regimen must also adhere to the guidelines specified above for the first induction. Please refer to [Section 7.2.1](#).

Patients who have achieved a CR/CRI after the second cycle may continue with the consolidation phase; all other patients should be removed from protocol.

Patients may start consolidation treatment at least 3 days and no later than 42 calendar days after the last midostaurin dose of induction.

An end phase disposition will be completed prior the C1D1 of the consolidation phase.

7.1.4.2 Consolidation phase

Patients who achieved a CR/CRI after either one or two induction cycles will receive consolidation therapy with cytarabine as defined by NCCN treatment guidelines plus subsequent midostaurin during each cycle. Patients will receive up to four cycles of consolidation therapy. Fewer cycles are accepted as per investigator’s discretion.

Each consolidation cycle is 28 days treatment. It is recommended that subsequent cycle start at least 3 days after the previous cycle is completed and no later than 70 calendar days from the start of the first cycle of consolidation. For the other consolidation cycles a recovery periods of 21 days maximum will be applied. Refer to [Table 6-2](#) for consolidation treatment schedule.

An end phase disposition will be completed prior the C1D1 of the maintenance phase.

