10.5.3.2 Adverse events (AEs)

Summary tables for adverse events (AEs) will include only AEs that started or worsened during the on-treatment period, the **treatment-emergent** AEs.

The incidence of treatment-emergent adverse events (new or worsening from baseline) will be summarized by system organ class, preferred term, severity (based on CTCAE grades), type of AE, relation to study treatment, periods and regimens as specified above and overall. AEs with different starts dates in different periods will be counted within each period.

AEs leading to discontinuation, serious AEs (SAE) and non-SAEs during the on-treatment period will be tabulated by type of AE.

All deaths (on-treatment and post-treatment) reportable as SAEs and non-fatal SAEs will be listed by patient and tabulated by type of AE.

All AEs, deaths and SAEs (including those from the pre and post-treatment periods) will be listed and those collected during the pre-treatment and post-treatment period will be flagged.

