#### 2.1.1 General definitions

The overall observation period is divided into the following **mutually exclusive** periods:

1. **Pre-treatment:** from day of patient's informed consent to the day before first dose of midostaurin

2. **On-treatment:** from start date of midostaurin to last date of study treatment + 30 days.

Further details provided in [Section 2.1.3](#).

On-treatment includes 3 mutually exclusive periods:

- a. **Induction** period: From day of first dose of midostaurin to the day before start of consolidation period (i.e. end of induction phase plus any rest/recovery days).  
Up to 2 cycles (28 days of treatment/cycle and a recovery period)
- b. **Consolidation** period: From day of first dose of study treatment in consolidation phase to the day before start of maintenance (i.e. end of consolidation phase plus any rest/recovery days).  
Up to 4 cycles (28 days of treatment/cycle and a recovery period)
- c. **Maintenance** period: From day of first dose of midostaurin in the maintenance phase to the date of last dose of midostaurin + 30 days.  
Up to 12 cycles (28 days of treatment/cycle)

It is noted that if a patient permanently discontinues study treatment during any of these periods, on-treatment is considered until the date of last dose of study treatment + 30 days (unless patient withdraws study informed consent or dies before then, then it is till the withdrawal/death date)

3. **Post-treatment:** from last date of study treatment + 31 days to end of study

Each period will contain all patients who entered that period (incl. withdrawal, drop-outs etc.)

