## **2.9 Safety analyses**

The primary objective is to further assess the safety of midostaurin in induction, consolidation and maintenance therapy including the ‘7+3’ regimen, daunorubicin (60-90mg/m^2/day), the substitution of daunorubicin by idarubicin (12 mg/m^2/day) and cytarabine (100-200 mg/m^2/day) and also allowing the “5+2” reduced dose regimen.

Except for baseline values, safety summary tables will only include on-treatment assessments (up to 30 days after study treatment discontinuation) and will be based on the safety set. Listings will include all data and will be based on the safety set.

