### 2.9.4.2 Cardiac imaging

The left ventricular ejection fraction (LVEF) data will be summarized for change from baseline to the worst on-treatment value by period and overall for the safety set. A listing will be provided showing the imaging method (multi gated acquisition scan (MUGA) or echocardiogram), date of assessment, LVEF percentage, the overall interpretation (normal, clinically insignificant abnormality or clinically significant abnormality) and the corresponding ejection fraction CTCAE v4.03 grades. Records outside of on-treatment period will be flagged.

Grades:

- Grade 0: Non missing value below Grade 2
- Grade 1: NA
- Grade 2: 50-40% or 10-19% drop from baseline i.e.
  - $40\% \leq \text{LVEF} \leq 50\%$  or  $-20\% < \text{absolute change from baseline} \leq -10\%$
- Grade 3: 39-20% or ≥20% drop from baseline i.e.
  - $20\% \leq \text{LVEF} < 40\%$  or  $\text{absolute change from baseline} \leq -20\%$
- Grade 4: <20% i.e.
  - $\text{LVEF} < 20\%$

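### Permitted recovery can outlast the last-dose + 30-day window, so a new non-fatal event in the gap is tabulated only if the patient later restarts

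*Protocol*

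**What the plan says.** Restart limits differ by step.

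- **Induction cycle 1 to 2** (Protocol 7.1.4.1): "treatment will begin at least 3 days and no later than 42 calendar days after completing midostaurin".
- **Induction to consolidation** (Protocol 7.1.4.1): "no later than 42 calendar days after the last midostaurin dose of induction".
- **Consolidation cycle 1 to 2** (Protocol 7.1.4.2): recommended "no later than 70 calendar days from the start of the first cycle of consolidation".
- **Later consolidation cycles** (Protocol 7.1.4.2): at most 21 days of recovery.
- **Consolidation to maintenance** (Protocol 7.1.4.3): at most 28 days after the last midostaurin dose.

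The analysis window follows two rules. For a patient who goes on, SAP 2.1.1 runs the induction period to the day before consolidation, that is, "end of induction phase plus any rest/recovery days"; consolidation is handled in the same way. For a patient who permanently stops, "on-treatment is considered until the date of last dose of study treatment + 30 days", or to withdrawal of consent or death if earlier. Protocol 10.5.3.1 has the same pair of rules. SAP 2.1.3 includes both ends of the window, and day +31 onward is post-treatment.

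Protocol 10.5.3.2 then states: "Summary tables for adverse events (AEs) will include only AEs that started or worsened during the on-treatment period". SAP 2.9 limits safety summary tables to on-treatment data in the same way, and events outside the window are listed and flagged. LVEF is "summarized for change from baseline to the worst on-treatment value by period and overall for the safety set" (SAP 2.9.4.2). SAP 2.7.1 ties CR/CRi to on-treatment assessments.

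**The concern.** Whether an event in late recovery is on-treatment depends on what happens to the patient afterwards. Take a non-fatal grade 3 event that starts 35 days after the last induction dose. If the patient starts consolidation on day +40, the event is in the summary tables. If the event is the reason the patient never starts consolidation, it is only listed. Yet the second case is the one that the table of adverse events leading to discontinuation exists to show, and that proportion is part of the primary endpoint (Protocol Table 3-1).

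Two other results share the problem:

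- **LVEF.** The End of Treatment visit follows the decision to stop (Protocol 7.1.5), which may properly come after day +30. The mandatory LVEF at that visit may be the patient's only post-baseline value, because Protocol Table 7-1 otherwise asks for imaging only when justified or at the physician's discretion.
- **CR/CRi.** Protocol 7.2.1 times the confirmatory marrow to count recovery. A slow recoverer who is documented in CR after day +30 and then leaves for transplant has that assessment outside the window. An earlier CRi may still count.

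The trial has a single arm, so no comparator would reveal the loss.

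**Working it through.** **The plan's own figure.** The chance of at least one event at 1% incidence with 300 patients is 1 − 0.99^300 = 0.9510, as in Protocol Table 10-1. The point raised here does not change it.

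**Inputs.** The last covered day is +30 (SAP 2.1.3). Recovery ends the day before restart (SAP 2.1.1). The restart limits are those of Protocol 7.1.4.1 to 7.1.4.3. Midostaurin normally ends on cycle day 28 (Protocol Tables 6-1 and 6-2). Let L be the cycle day of the last dose of any study treatment.

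**Formula.** If the latest restart is R days after the last dose, uncovered days = (R − 1) − 30, or zero if that is negative.

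| Step | Latest restart | Last covered day | Uncovered days |
|---|---|---|---|
| Induction 1 to 2; induction to consolidation | +42 | +30 | 41 − 30 = 11 (+31 to +41) |
| Consolidation 1 to 2, L = 28 | cycle day 70 (71) | 58 | 11 (12) |
| same, L = 21 | 70 (71) | 51 | 18 (19) |
| same, L = 14 | 70 (71) | 44 | 25 (26) |
| same, cytarabine only, L = 5 | 70 (71) | 35 | 34 (35) |
| Consolidation to maintenance | +28 | +30 | 0 |

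Figures in brackets read the limit as start + 70 days. For consolidation cycle 1 the general form is 39 − L (40 − L). After induction the uncovered share is 11/41 = 27%.

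**Consolidation cycles 2 and 3.** With 21 recovery days after cycle day 28, the latest restart is day 50, so the gap is 49 − (L + 30) = 19 − L. It is zero for L = 19 or later, 1 day for L = 18, 5 for L = 14 and 14 for L = 5.

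**The 56-day rule.** Protocol 7.2.1 asks sites to contact the sponsor if a consolidation cycle is delayed more than 56 days from the start of the previous one. A restart at start + 56 (cycle day 57) leaves 56 − (L + 30) = 26 − L days: zero for L = 28, 5 for L = 21 and 12 for L = 14.

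**Scale only.** SAP section 1 reports 301 enrolled. One non-restarter whose first qualifying event falls in the gap moves a whole-study proportion by 1/301 = 0.33 percentage points. Three such patients move it by 3/301 = 1.0 point. The documents give no rates of non-restart or of events in late recovery, so the true number cannot be computed.

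**The case against.** A cut-off at last dose + 30 days is prespecified and consistent across both documents, and no hypothesis is tested. Most late toxicity is already covered: an event that began by day +30 is counted unless the concern is a later worsening, all deaths have their own table (SAP 2.9.1), and everything else is listed and flagged. What is left is a new or worsened non-fatal event in a patient more than 30 days off drug who never restarts. Such patients also stop for transplant, relapse or lack of remission (Protocol 4.3, 7.1.4.1, 7.1.5), so a late event may reflect disease or later therapy. A patient-level proportion changes only if the patient had no earlier event of that type. The 70-day limit is a recommendation. Protocol 7.2.1 also expects consolidation cycles within two weeks of count recovery, with sponsor contact after 56 days.

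All of this stands, and it narrows the point. It makes the consolidation figures outer bounds. It does not touch the two induction gaps, and it does not forbid later consolidation restarts. Nor does it answer the case of an event that itself prevents restart.

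Protocol 10.5.3.2 might be read as tabulating post-treatment non-fatal SAEs as well, which would partly close the gap. SAP 2.9 does not carry that reading through.

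A reader might infer that the primary safety results materially understate toxicity, or that slow recoverers' events vanish from the report. The documents support neither inference: the number affected is unknown, the events remain in listings, and slow recovery that began by day +30 is tabulated.

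**Conclusion.** The asymmetry is in the text of both documents. With restart at the permitted limit, 11 of 41 recovery days after either induction cycle lie outside the window for non-restarters. After consolidation cycle 1 it is 11 or 12 days with full dosing and about 39 − L to 40 − L days with early stopping. After consolidation cycles 2 and 3 a gap opens only if the last dose was on about day 18 or earlier. None arises before maintenance.

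The consequence is confined to new or worsened non-fatal AEs and SAEs, AEs leading to discontinuation, and End of Treatment LVEF or CR/CRi marrow results that fall in those days. The exclusion depends on outcome and leans towards leaving out events that stopped treatment. Its size is unknown and may be small, so this is a low-cost improvement and not a flaw that undermines the analysis. The day counts assume that the 21-day recovery runs from cycle day 28 and that sites use the full permitted interval.

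**What to change.** Keep the + 30-day tables. In SAP 2.1.1 and 2.1.3 add a supplementary on-treatment definition for patients who do not restart after any induction or consolidation cycle:

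- End it at the later of last dose + 30 days and the recorded discontinuation (End of Treatment visit or death).
- Cap any extension at the day before that cycle's own latest permitted restart: day +41 after induction, cycle day 69 (or 70, once the limit is clarified) after consolidation cycle 1, and cycle day 49 after later consolidation cycles followed by another. The cap never shortens the + 30-day window.
- Apply it to the AE, SAE, LVEF and CR/CRi summaries, and above all to AEs leading to discontinuation, where any AE recorded as the reason for not restarting should be counted.
- Footnote how many patients are extended and by how many days.

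The cost is one definition and a rerun of those tables. AEs are recorded continuously (Protocol Table 7-1), and the patient remains under study observation until the final visit (Protocol 7.1.5).

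There are limits. The window length would depend on when discontinuation is recorded, so some outcome dependence remains. Non-serious AEs and unrelated SAEs need not be collected beyond 30 days after the last dose (Protocol 7.1.7, 8.1.1, 8.2.2), so capture may be incomplete. The latest SAP revision already follows database lock, so the new tables should be labelled post hoc.
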